### **8.5 Aseptic meningitis**

Definition: may present with headache, photophobia, and neck stiffness; often afebrile but may be febrile. There may be nausea/vomiting. Mental status should be normal (distinguishes from encephalitis).

Diagnostic work-up

MRI of brain with or without contrast + pituitary protocol AM cortisol, ACTH to rule out adrenal insufficiency

Consider lumbar puncture: measure opening pressure; check cell count and protein glucose; and perform Gram stain, culture, PCR for HSV, and other viral PCRs depending on suspicion, cytology

8.0 Nervous System Toxicities	
May see elevated WBC count with normal glucose, normal culture, and Gram stain; may see reactive lymphocytes or histiocytes on cytology	
Grading	Management

G1: Mild, no interference with function and symptoms not concerning to patient. Note: Any cranial nerve problem should be managed as moderate.
 
G2: Moderate, some interference with ADL, symptoms concerning to patient (ie, pain but no weakness or gait limitation)
 
G3-4: Severe, limiting self-care and aids warranted
	
Hold ICPi and discuss resumption with patient only after taking into account the risks and benefits, consider empirical antiviral (IV acyclovir) and antibacterial therapy until CSF results. Once bacterial and viral infection are negative, may closely monitor off corticosteroids or consider oral prednisone 0.5-1 mg/kg or IV methylprednisolone 1 mg/kg if moderate/severe symptoms

8.6 Encephalitis	

Definition: As for aseptic meningitis, need to exclude infectious causes, especially viral (ie, HSV). Confusion, altered behavior, headaches, seizures, short-term memory loss, depressed level of consciousness, focal weakness, speech abnormality
	

Diagnostic work-up
 
Neurologic consultation
 
MRI of brain with or without contrast may reveal T2/fluid-attenuated inversion recovery changes typical of what is seen in autoimmune encephalopathies or limbic encephalitis or may be normal
 
Lumbar puncture: check cell count and protein glucose and perform Gram stain, culture, PCR for HSV and other viral PCRs depending on suspicion, cytology, oligoclonal bands, autoimmune encephalopathy, and paraneoplastic panels.
 
May see elevated WBC count with lymphocytic predominance and/or elevated protein EEG to evaluate for subclinical seizures
 
Blood: metabolic, CBC, ESR, CRP, ANCA (if suspect vasculitic process), thyroid panel including TPO and thyroglobulin. Rule out concurrent anemia/thrombocytopenia, which can present with severe headaches and confusion
	
Grading	Management

G1: Mild, no interference with function and symptoms not concerning to patient. Note: Any cranial nerve problem should be managed as moderate.
 
G2: Moderate, some interference with ADL, symptoms concerning to patient (ie, pain but no weakness or gait limitation)
 
G3-4: Severe, limiting self-care and aids warranted
	
Hold ICPi and discuss resumption with patient only after taking into account the risks and benefits
 
As above for aseptic meningitis suggest concurrent IV acyclovir until PCR results obtained and negative
 
Trial of methylprednisolone 1-2 mg/kg
 
If severe or progressing symptoms or oligoclonal bands present, consider pulse corticosteroids methylprednisolone 1 g IV daily for 3-5 days plus IVIG 2 g/kg over 5 days. If positive for autoimmune encephalopathy antibody and limited or no improvement, consider rituximab or plasmapheresis in consultation with neurology.

8.7 Transverse myelitis	
Definition: Acute or subacute weakness or sensory changes bilateral, often with increased deep tendon reflexes	
Diagnostic work-up	
Neurologic consultation	
MRI of spine (with thin axial cuts through the region of suspected abnormality) and MRI of brain	
Lumbar puncture: cell count, protein, glucose, oligoclonal bands, viral PCRs, cytology, onconeural antibodies	
Blood: B12, HIV, RPR, ANA, Ro/La, TSH, aquaporin-4 IgG	
Evaluation for urinary retention, constipation	
Grading	
G1: Mild, no interference with function and symptoms not concerning to patient. Note: Any cranial nerve problem should be managed as moderate.	
Management	
Permanently discontinue ICPi Methylprednisolone 2 mg/kg	

8.0 Nervous System Toxicities	
G2: Moderate, some interference with ADL, symptoms concerning to patient (ie, pain but no weakness or gait limitation)	Strongly consider higher doses of 1 g/d for 3-5 days Strongly consider IVIG
G3-4: Severe, limiting self-care and aids warranted	

All recommendations are expert consensus based, with benefits outweighing harms, and strength of recommendations are moderate.

Abbreviations: AChR, acetylcholine receptor; ACTH, adrenocorticotropic hormone; ADL, activities of daily living; ANA, antinuclear antibody; ANCA, antineutrophil cytoplasmic antibodies; CBC, complete blood count; CNS, central nervous system; CPK, creatine phosphokinase; CRP, C-reactive protein; CSF, cerebrospinal fluid; ECG, electrocardiogram; EEG, electroencephalogram; EMG, electromyography; ESR, erythrocyte sedimentation rate; G, Grade; GI, gastrointestinal; HIV, human immunodeficiency virus; HSV, herpes simplex virus; ICPI, immune checkpoint inhibitor; ICU, intensive care unit; IgG, immunoglobulin G; IV, intravenous; IVIG, intravenous immunoglobulin; irAE, immune- related adverse event; MGFA, Myasthenia Gravis Foundation of America; MRI, magnetic resonance imaging; NA, not applicable; NCS, nerve conduction study; NIF, negative inspiratory force; PCR, polymerase chain reaction; RPR, rapid plasma reagin, TPO, thyroid peroxidase; TSH, thyroid-stimulating hormone; TTE, transthoracic echocardiogram; VC, vital capacity; WBC, white blood cell count.

**MANAGEMENT OF HEMATOLOGIC irAES IN PATIENTS TREATED WITH ICPis**

9.0 Hematologic Toxicities	
9.1 Autoimmune hemolytic anemia	
Definition: A condition in which RBCs are destroyed and removed from the blood stream before their normal lifespan is over. Symptoms include weakness, paleness, jaundice, dark-colored urine, fever, inability to do physical activity, and heart murmur.	
Diagnostic work-up	
History and physical examination (with special consideration of history of new drugs and insect, spider, or snake bites)	
Blood chemistry, CBC with evidence of anemia, macrocytosis, evidence of hemolysis on peripheral smear; LDH, haptoglobin, bilirubin, reticulocyte count, free Hgb DIC panel, which could include PTNIR infectious causes	
Autoimmune serology	
Paroxysmal nocturnal hemoglobinuria screening	
Direct and indirect bilirubin; LDH; direct agglutinin test; and if no obvious cause, bone marrow analysis, cytogenetic analysis to evaluate for myelodysplastic syndromes	
Evaluation for viral/bacterial (mycoplasma, etc) causes of hemolysis studies Protein electrophoresis, cryoglobulin analysis	
Work-up for bone marrow failure syndrome if refractory, including B12, folate, copper, parvovirus, FE, thyroid, infection	
Glucose-6-phosphate dehydrogenase	
Evaluation of common drug causes (ribavirin, rifampin, dapsone, interferon, cephalosporins, penicillins, NSAIDs, quinine/quinidine, fludarabine, ciprofloxacin, lorazepam, diclofenac, etc)	
Assessment of methemoglobinemia	
Grading	
G1: Hgb < LLN to 10.0 g/dL; < LLN to 6.2 mmol/L; < LLN to 100 g/L	
Continue ICPi with close clinical follow-up and laboratory evaluation	
G2: Hgb < 10.0 to 8.0 g/dL; < 6.2 to 4.9 mmol/L; < 100 to 80 g/L	
Hold ICPi and strongly consider permanent discontinuation	
Administer 0.5-1 mg/kg/d prednisone equivalents	

G3: Hgb < 8.0 g/dL; < 4.9 mmol/L; < 80 g/L; transfusion indicated	
Permanently discontinue ICPi          Should use clinical judgment and consider admitting the patient          Hematology consult          Prednisone 1-2 mg/kg/d (oral or IV depending on symptoms/speed of development)          If worsening or no improvement, 1-2 mg/kg/d prednisone equivalents and permanently discontinue ICPi treatment          Consider RBC transfusion per existing guidelines; do not transfuse more than the minimum number of RBC units necessary to relieve symptoms of anemia or to return a patient to a safe Hgb range (7-8 g/dL in stable, noncardiac inpatients)          Should offer patients supplementation with folic acid 1 mg once daily

G4: Life-threatening consequences, urgent intervention indicated	
Permanently discontinue          ICPi          Admit patient          Hematology consult          IV prednisone corticosteroids 1-2 mg/kg/d

9.0 Hematologic Toxicities	
	
If no improvement or if worsening while on corticosteroids or severe symptoms on presentation, initiate other immunosuppressive drugs, such as rituximab, IVIG, cyclosporin A, and mycophenolate mofetil
 
RBC transfusion per existing guidelines; discuss with blood bank team prior to transfusions that a patient with possible ICPi serious AE is in house.

Additional considerations: Monitor Hgb levels on a weekly basis until the corticosteroid tapering process is complete; thereafter, less-frequent testing is needed	
9.2 Acquired TTP	
Definition: A disorder characterized by the presence of microangiopathic hemolytic anemia, thrombocytopenic purpura, fever, renal abnormalities, and neurologic abnormalities, such as seizures, hemiplegia, and visual disturbances. It is an acute or subacute condition.	

Diagnostic work-up
 
History with specific questions related to drug exposure (eg, chemotherapy, sirolimus, tacrolimus, opana ER antibiotics, quinine) Physical examination, peripheral smear
 
ADAMTS13 activity level and inhibitor titer
 
LDH, haptoglobin, reticulocyte count, bilirubin, urinalysis to rule out other causes
 
PT, activated PTT, fibrinogen
 
Blood group and antibody screen, direct antiglobulin test, CMV serology
 
Consider CT/MRI brain, echocardiogram, ECG
 
Viral studies
 
Note: This disorder is usually associated with a severe drop in platelets and hemolysis/anemia precipitously
	
Grading	Management
All grades	
The first step in the management of TTP is a high index of suspicion for the diagnosis and timely recognition; hematology consult should immediately be called, as delay in identification is associated with increased mortality/morbidity.
 
Initially, the patient should be stabilized and any critical organ dysfunction stabilized

G1: Evidence of RBC destruction (schistocytosis) without anemia, renal insufficiency, or thrombocytopenia clinically  G2: Evidence of RBC destruction (schistocytosis) without clinical consequence with G2 anemia and thrombocytopenia	
Hold ICPi and discuss resumption with patient only after taking into account the risks and benefits, noting that there are currently no data to recommend restarting ICPi therapy
 
Hematology consult
 
Administer 0.5-1 mg/kg/d prednisone

G3: Laboratory findings with clinical consequences (G3 thrombocytopenia, anemia, renal insufficiency > 2)
 
G4: Life-threatening consequences (eg, CNS hemorrhage or thrombosis/embolism or renal failure)
	
For G3: Hold ICPi and discuss resumption with patient only after taking into account the risks and benefits, noting that there are currently no data to recommend restarting ICPi therapy
 
For G4: permanently discontinue ICPi
 
Hematology consult
 
In conjunction with hematology, initiate PEX according to existing guidelines with further PEX dependent on clinical progress
 
Administer methylprednisolone 1 g IV daily for 3 days, with the first dose typically administered immediately after the first PEX
 
May offer rituximab
 
In case of management with rituximab, ICPi treatment will be discontinued

---	--

9.0 Hematologic Toxicities													
9.3 Hemolytic uremic syndrome													

Definition: A disorder characterized by a form of thrombotic microangiopathy with renal failure, hemolytic anemia, and severe thrombocytopenia. Signs and symptoms of hemolytic uremic syndrome can include:
 
Bloody diarrhea
 
Decreased urination or blood in the urine
 
Abdominal pain, vomiting, and occasionally fever
 
Pallor
 
Small, unexplained bruises or bleeding from the nose and mouth
 
Fatigue and irritability
 
Confusion or seizures
 
High blood pressure
 
Swelling of the face, hands, feet, or entire body
													

Diagnostic work-up
 
History and physical examination (special consideration for new history of high-risk drugs, hypertension, or cardiac causes)
 
CBC with indices
 
Blood smear morphology. Note that the presence of schistocytes on smear is critical for diagnosis.
 
Serum creatinine
 
ADAMTS13 (to rule out TTP)
 
Homocysteine/methylmalonic acid
 
Complement testing C3, C4, CH50 (complement inhibitory antibodies for suspected familial)
 
Evaluate reticulocyte count and mean corpuscular volume
 
Evaluation of infectious cause, including screening for EBV, CMV, HHV6
 
Evaluation for nutritional causes of macrocytosis (B12 and folate)
 
Pancreatic enzymes
 
Evaluation for diarrheal causes, shiga toxin, Escherichia coli 0157, etc
 
Direct antibody test (Coombs test), haptoglobin, LDH, and other etiologies of anemia
 
Evaluation for common drugs causing hemolysis (tacrolimus, cyclosporine, sirolimus, etc)
 
Evaluation for concurrent confusion
													

  
 Grading	Management	
   
 G1-2: Evidence of RBC destruction (schistocytosis) without clinical consequences of anemia, thrombocytopenia	For G1 and G2: Continue ICPI with close clinical follow-up and laboratory evaluation	
 
 Grade 2	Supportive care	
 
 G3: Laboratory findings with clinical consequences (eg, renal insufficiency, petechiae)	For G3 and G4: Permanently discontinue ICPI	
 
 G4: Life-threatening consequences (eg, CNS thrombosis/ embolism or renal failure)	Begin therapy with eculizumab therapy 900 mg weekly for four doses, 1,200 mg week 5, then 1,200 mg every 2 weeks	
 
 	Red blood transfusion according to existing guidelines	
  
		Grading	Management	G1-2: Evidence of RBC destruction (schistocytosis) without clinical consequences of anemia, thrombocytopenia	For G1 and G2: Continue ICPI with close clinical follow-up and laboratory evaluation	Grade 2	Supportive care	G3: Laboratory findings with clinical consequences (eg, renal insufficiency, petechiae)	For G3 and G4: Permanently discontinue ICPI	G4: Life-threatening consequences (eg, CNS thrombosis/ embolism or renal failure)	Begin therapy with eculizumab therapy 900 mg weekly for four doses, 1,200 mg week 5, then 1,200 mg every 2 weeks		Red blood transfusion according to existing guidelines
Grading	Management												
G1-2: Evidence of RBC destruction (schistocytosis) without clinical consequences of anemia, thrombocytopenia	For G1 and G2: Continue ICPI with close clinical follow-up and laboratory evaluation												
Grade 2	Supportive care												
G3: Laboratory findings with clinical consequences (eg, renal insufficiency, petechiae)	For G3 and G4: Permanently discontinue ICPI												
G4: Life-threatening consequences (eg, CNS thrombosis/ embolism or renal failure)	Begin therapy with eculizumab therapy 900 mg weekly for four doses, 1,200 mg week 5, then 1,200 mg every 2 weeks												
	Red blood transfusion according to existing guidelines												
8.4 Aplastic anemia													

Definition: Condition in which the body stops producing enough new blood cells
													

**Diagnostic work-up**

History and physical examination (close attention to medications, exposure to radiation, toxins, recent viral infections) CBC, smear, reticulocyte count

Viral studies, including CMV, HHV6, EBV, parvovirus

Nutritional assessments including B12, folate, iron, copper, ceruloplasmin, vitamin D Serum LDH, renal function

Work-up for infectious

causes Identify marrow

hypo/aplasia

Bone marrow biopsy and aspirate analysis

Peripheral blood analysis, including neutrophil count, proportion of GPI-negative cells by flow for PNH Flow cytometry to evaluate loss of GPI-anchored proteins

9.0 Hematologic Toxicities	
Type and screen patient for transfusions and notify blood bank that all transfusions need to be irradiated and filtered	
Grading	Management
G1: Nonsevere, < 0.5 polymorphonuclear cells $\times 10^9/L$ hypocellular marrow, with marrow cellularity < 25%, peripheral platelet count > 20,000, reticulocyte count < 20,000	Hold ICPi and provide growth factor support and close clinical follow-up, and laboratory evaluation Supportive transfusions as per local guidelines
G2: Severe, hypocellular marrow < 25% and two of the following: ANC < 500, peripheral platelet < 20,000, and reticulocyte < 20,000	Hold ICPi and provide growth factor support and close clinical laboratory evaluations daily Administer ATG + cyclosporine; HLA typing and evaluation for bone marrow transplantation if patient is candidate; all blood products should be irradiated and filtered Supportive care with granulocyte colony-stimulating factor may be added in addition
G3-4: Very severe, ANC > 200, platelet count > 20,000, reticulocyte count > 20,000, plus hypocellular marrow > 25%	For G3: Hold ICPi and monitor weekly for improvement; if not resolved, discontinue treatment until AE has reverted to G1 For G4: permanently discontinue ICPi Hematology consult, growth factor support Horse ATG plus cyclosporine If no response, repeat immunosuppression with rabbit ATG plus cyclosporine, cyclophosphamide For refractory patients, consider eltrombopag plus supportive care
9.5 Lymphopenia	
Definition: An abnormally low level of lymphocytes in PB; for adults, counts of < 1,500/mm 	
Diagnostic work-up	
History and physical examination (special attention for lymphocyte-depleting therapy such as fludarabine, ATG, corticosteroids, cytotoxic chemotherapy, radiation exposure, etc, as well as history of autoimmune disease, family history of autoimmune disease) Evaluation of nutritional state as cause	
Spleen size	
CBC with differential, peripheral smear and reticulocyte counts CXR for evaluation of presence of thymoma	
Bacterial cultures and evaluation for infection (fungal, viral, bacterial specifically CMV/HIV)	

Grading	Management
G1-2: 500-1,000 PB lymphocyte count    G3: 250-499 PB lymphocyte count G4: < 250 PB lymphocyte count	Continue ICPi for G1 to G2 For G3 single laboratory values out of normal range without any clinical correlates, hold treatment until resolution to G1 For G4, for single laboratory values out of normal range without any clinical correlates, permanent treatment discontinuation is not required. Treatment should be held until the etiology is determined. Permanent treatment discontinuation will only be required, if lymphopenia is considered of immune related in nature, no clear alternative explanation exists for the event, and grade 4 lymphopenia does not resolve within 14 days. If the event is not considered immune related and resolves to G $\leq$ 1 restarting treatment may be considered.

9.0 Hematologic Toxicities	
	
Check CBC weekly for monitoring, initiation of CMV screening Consider holding ICPi
 
Initiate Mycobacterium avium complex prophylaxis and Pneumocystis jirovecii prophylaxis, CMV screening. HIV/hepatitis screening if not already done
 
May consider EBV testing if evidence of lymphadenopathy/hepatitis, fevers, hemolysis consistent with lymphoproliferative disease.

9.6 Immune thrombocytopenia	
Definition: An autoimmune disorder characterized by immunologic destruction of otherwise normal platelets	

Diagnostic work-up
 
History and physical examination (special attention for lymphocyte-depleting therapy, such as fludarabine, ATG, corticosteroids, cytotoxic therapy) Family history of autoimmunity or personal history of autoimmune disease
 
History of viral illness
 
CBC
 
Peripheral blood smear, reticulocyte count
 
Bone marrow evaluation only if abnormalities in the above test results and further investigation is necessary for a diagnosis
 
Patients with newly diagnosed immune thrombocytopenia should undergo testing for HIV, hepatitis C virus, hepatitis B virus, and Helicobacter pylori Direct antigen test should be checked to rule out concurrent Evan syndrome
 
Nutritional evaluation
 
Bone marrow evaluation if other cell lines affected and concern for aplastic anemia
	
Grade	Management
G1: Platelet count < 100/ $\mu$ L G2: Platelet count < 75/ $\mu$ L	
Continue ICPi with close clinical follow-up and laboratory evaluation
 
Hold ICPi but monitor for improvement; if not resolved, interrupt treatment until AE has reverted to G1
 
Administer prednisone 1 mg/kg/d (dosage range, 0.5-2 mg/kg/d) orally for 2-4 weeks after which time this medication should be tapered over 4-6 weeks to the lowest effective dose IVIG may be used in conjunction with corticosteroids if a more-rapid increase in platelet count is required.

G3: Platelet count < 50/ $\mu$ L	Hold ICPi but monitor for improvement; if not resolved, interrupt treatment until AE has reverted to G1

G4: Platelet count < 25/ $\mu$ L	
Permanently discontinue ICPi
 
Hematology consult
 
Prednisone 1-2 mg/kg/d (oral or IV depending on symptoms)
 
If worsening or no improvement, 1-2 mg/kg/d prednisone equivalents and permanently discontinue treatment
 
IVIG used with corticosteroids when a more-rapid increase in platelet count is required
 
If IVIG is used, the dose should initially be 1 g/kg as a one-time dose. This dosage may be repeated if necessary

----------------------------------	---

9.0 Hematologic Toxicities	
	If previous treatment with corticosteroids and/or IVIG unsuccessful, subsequent treatment may include rituximab, thrombopoietin receptor agonists, or more-potent immunosuppression (From American Society of Hematology guideline on immune thrombocytopenia  ; consult for further details)
9.7 Acquired hemophilia	
Definition: Disorder caused by the development of autoantibodies (inhibitors) directed against plasma coagulation factors	
Diagnostic work-up	Full blood count to assess platelet number, fibrinogen, PT, PTT, INR; the typical finding in patients with acquired hemophilia A is a prolonged activated PTT with a normal PT
	MRI, CT, and ultrasonography may be indicated to localize, quantify, and serially monitor the location and response of bleeding Medication review to assess for alternative causes
Determination of Bethesda unit level of inhibitor	
Grading	Management
G1: Mild, 5%-40% of normal factor activity in blood, 0.05-0.4 IU/mL of whole blood	Hold ICPi and discuss resumption with patient only after taking into account the risks and benefits Administer 0.5-1 mg/kg/d prednisone Transfusion support as required Treatment of bleeding disorders with hematology consult
G2: Moderate, 1%-5% of normal factor activity in blood, 0.01- 0.05 IU/mL of whole blood	Hematology consult Administration of factor replacement (choice based on Bethesda unit of titer) Administer 1 mg/kg/d prednisone ± rituximab (dose, 375 mg/m  weekly for 4 weeks) and/or cyclophosphamide (dose, 1-2 mg/kg/d); choice of rituximab v cyclophosphamide is patient specific and should be done with assistance of hematology consult; prednisone, rituximab, and cyclophosphamide should be given for at least 5 weeks Factors should be provided to increase level during bleeding episodes, with choice of factor based on presence or absence of inhibitor

G3-4: Severe, < 1% of normal factor activity in blood, < 0.01 IU/mL of whole blood	
Permanently discontinue ICPi Admit patient Hematology consult Administration of factor replacement, choice based on Bethesda unit level of inhibitor Bypassing agents may be used (factor VII, factor VIII inhibitor bypass activity); caution should be taken in the elderly and those with coronary artery disease Prednisone 1-2 mg/kg/d (oral or IV depending on symptoms) ± rituximab (dose, 375 mg/m^2 weekly for 4 weeks) and/or cyclophosphamide (dose, 1-2 mg/kg/d). Transfusion support as required for bleeding If worsening or no improvement add cyclosporine or immunosuppression/immunoabsorption

Additional considerations: The American Heart Association requires specialist clinical and laboratory expertise. Consult and/or transfer to a specialist center is often appropriate. If consultation with or transfer to a hemophilia center is not immediately possible, then investigation and treatment should be initiated while a liaison is being established.	

9.0 Hematologic Toxicities
All recommendations are expert consensus based, with benefits outweighing harms, and strength of recommendations are moderate.

All recommendations are expert consensus based, with benefits outweighing harms, and strength of recommendations are moderate.

Abbreviations: AE, adverse event; ANC, absolute neutrophil count; ATG, antithymocyte globulin; CBC, complete blood count; CMV, cytomegalovirus; CNS, central nervous system; CT, computed tomography; CXR, chest x-ray; DIC, disseminated intravascular coagulation; EBV, Epstein-Barr virus; ECG, electrocardiogram; ER, extended release; FE, ferritin; G, Grade; GPI, glycosylphosphatidylinositol; Hgb, hemoglobin; HHV6, human herpesvirus 6; HIV, human immunodeficiency virus; HLA, human leukocyte antigen; ICPi, immune checkpoint inhibitor; INR, international normalized ratio; irAE, immune-related adverse event; IV, intravenous; IVIG, intravenous immunoglobulin; LDH, lactate dehydrogenase; LLN, lower limit of normal; MRI, magnetic resonance imaging; NSAID, nonsteroidal anti- inflammatory drug; PB, peripheral blood; PEX, plasma exchange; PNH, paroxysmal nocturnal hemoglobinuria; PT, prothrombin time; PTT, partial thromboplastin time; RBC, red blood cell count; TTP, thrombotic thrombocytopenic purpura.

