#### **5.6.2 Dose Modifications for Bintrafusp Alfa as Single Agent**

No dose reductions are permitted in this study, but doses may be omitted based on persisting toxicity. Any adverse event suspected to be immune-related should be managed according to the guidance for management of irAEs

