#### **5.6.3 Adverse Drug Reaction Requiring Bintrafusp Alfa Discontinuation or Delays**

The following adverse reactions (ADRs) require permanent treatment discontinuation of bintrafusp alfa:

**Any Grade 4 ADRs require bintrafusp alfa treatment discontinuation** except for single laboratory values out of normal range that are unlikely related to trial treatment as assessed by the Investigator(s), do not have any clinical correlate, and resolve within 7 days with adequate medical management.

**Any Grade 3 ADRs require bintrafusp alfa treatment discontinuation** except for any of the following:

- Transient ( $\leq$ 6 hours) Grade 3 flu-like symptoms or fever, which is controlled with medical management
- Transient ( $\leq$ 24 hours) Grade 3 fatigue, local reactions, headache, nausea, or emesis that resolves to Grade  $\leq$ 1
- Single laboratory values out of normal range (excluding Grade  $\geq$ 3 liver function test increase) that are unlikely related to trial treatment according to the Investigator(s), do not have any clinical correlate, and resolve to Grade  $\leq$ 1 within 7 days with adequate medical management
- Tumor flare phenomenon defined as local pain, irritation, or rash localized at sites of known or suspected tumor
- Change in Eastern Cooperative Oncology Group Performance Status (ECOG PS) to 3 that

resolve to  $\leq 2$  within 14 days (infusions should not be given on the following cycle, if the ECOG PS is 3 on the day of trial drug administration)

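### Two haematologic irAE tables in Section 5.6.5 are misprinted: the aplastic anaemia G3-4 limits have all four inequality signs reversed, and the immune thrombocytopenia limits carry a unit that makes them 1,000 times too low

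*Protocol*

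**What the plan says.** Section 5.6.2 of the Protocol sends investigators to the irAE guidance: "Any adverse event suspected to be immune-related should be managed according to the guidance for management of irAEs". Section 5.6.5 contains that guidance as a set of organ-system tables. Two entries in the haematologic table matter here.

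**Aplastic anaemia** (numbered 8.4, although it sits in table 9.0). G1 requires marrow cellularity below 25%. The next grade reads "G2: Severe, hypocellular marrow < 25% and two of the following: ANC < 500, peripheral platelet < 20,000, and reticulocyte < 20,000". The worst row then reads "G3-4: Very severe, ANC > 200, platelet count > 20,000, reticulocyte count > 20,000, plus hypocellular marrow > 25" per cent. The action for G3 in that merged row is "Hold ICPi and monitor weekly for improvement; if not resolved, discontinue treatment until AE has reverted to G1"; for G4 it is permanent discontinuation.

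**Immune thrombocytopenia** (9.6). The limits are "G1: Platelet count < 100", then below 75 for G2, "G3: Platelet count < 50" and "G4: Platelet count < 25", each printed per microlitre. The actions are continue at G1, hold at G2 (with prednisone) and G3, and permanent discontinuation at G4.

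For comparison, Section 3.1, criterion 11, sets the entry floors at ANC 1.5 x 10^9/L and platelets 100 x 10^9/L.

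**The concern.** A grading table should become harder to satisfy as the condition worsens. The aplastic anaemia table does the opposite at its last step: the most severe grade is defined by higher counts and a more cellular marrow than the grade below it. The platelet table runs in the right direction, but on a scale that does not match the rest of the Protocol.

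Both tables attach holding or stopping of study drug to their grades, and Section 5.6.2 makes them the place to look for a suspected immune-related event. Read literally, the numbers send a patient to the wrong row or to no row. What is at stake is contradictory instruction to investigators about dosing, not the trial's inference.

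**Working it through.** **Inputs.** The printed grade limits are from the Section 5.6.5 tables and the entry floors from Section 3.1. The aplastic anaemia table prints ANC without a unit. I take it as per microlitre, because the 0.5 x 10^9/L used for neutrophils in G1 then equals the 500 used in G2.

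**Conversion.** Count per microlitre = count per litre / 10^6.

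- ANC floor: 1.5 x 10^9 / 10^6 = 1,500 per microlitre.
- Platelet floor: 100 x 10^9 / 10^6 = 100,000 per microlitre.

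**Aplastic anaemia.** G2 needs marrow below 25% and printed G3-4 needs marrow above 25%, so no patient can satisfy both. As an assumed example of a very ill patient, take ANC 100, platelets 10,000, reticulocytes 10,000 and marrow 10%.

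| Measure | Value | Printed G2 | Printed G3-4 | G3-4, signs reversed |
|---|---|---|---|---|
| ANC | 100 | < 500: met | > 200: not met | < 200: met |
| Platelets | 10,000 | < 20,000: met | > 20,000: not met | < 20,000: met |
| Reticulocytes | 10,000 | < 20,000: met | > 20,000: not met | < 20,000: met |
| Marrow (%) | 10 | < 25: met | > 25: not met | < 25: met |
| Limits met | | 4 of 4 | 0 of 4 | 4 of 4 |

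At the other end, a patient at the entry floors has ANC 1,500 / 200 = 7.5 times the printed G3-4 limit and platelets 100,000 / 20,000 = 5 times. Two of the four limits for the worst grade are thus met at study entry. With the signs reversed, G3-4 nests inside G2, as it should.

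**Immune thrombocytopenia.** The G1 figure, read in the unit of Section 3.1, is 100 x 10^9/L = 100,000 per microlitre; 100,000 / 100 = 1,000. The same factor applies to 75, 50 and 25. Four illustrative counts:

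| Platelets (x 10^9/L) | Per microlitre | Multiple of printed G1 limit (100) | Grade as printed | Grade in x 10^9/L | Table action at that grade |
|---|---|---|---|---|---|
| 90 | 90,000 | 900 | none | G1 | continue |
| 60 | 60,000 | 600 | none | G2 | hold |
| 40 | 40,000 | 400 | none | G3 | hold |
| 20 | 20,000 | 200 | none | G4 | permanent stop |

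The table's own hold or stop is lost in three of the four cases.

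**The case against.** The best counter-argument is that the printed numbers rarely decide anything alone.

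- Section 6.1 grades all adverse events by CTCAE v4.0, and the general principle in Section 5.6.5 ties irAE treatment to CTCAE grade, so a platelet count has a grade without this table.
- Section 5.6.5 refers to the NCCN guideline for specific irAEs and separately requires a permanent stop for Grade 4 aplastic anaemia and Grade 4 immune thrombocytopenia.
- Section 5.6.3 states "Any Grade 4 ADRs require bintrafusp alfa treatment discontinuation", with a narrow exception for laboratory values. It also stops most Grade 3 reactions, and it holds and then stops Grade 2 reactions that do not resolve.
- For aplastic anaemia, printed G2 and corrected G3 both hold the drug, so no dosing decision is shown to change.
- A treating oncologist would recognise both misprints.

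Most of this stands, and it is why the point is minor. It does not make the tables right. For Grade 2 thrombocytopenia the backstop is also weaker than the table: the Grade 2 rule in Section 5.6.3 allows up to two weeks before a hold, while the table intends an immediate hold and prednisone. For aplastic anaemia, the unreachable row also carries treatment steps that G2 lacks, such as repeat immunosuppression and eltrombopag for refractory cases.

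A fault of text extraction is unlikely. Both inequality signs and the 10^9/L unit appear correctly in the same aplastic anaemia table, and the microlitre unit repeats on all four platelet grades.

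**Conclusion.** The concern holds, at minor severity. The aplastic anaemia G3-4 row cannot be reached from G2, because all four of its signs are reversed. The immune thrombocytopenia limits are 1,000 times too low at every grade, so the printed table never triggers its own hold or stop. The result is safety text that conflicts with other rules in the same Protocol, not a missing safeguard. The safety endpoint, the stopping rule in Section 7.3, the sample size and the analysis are unaffected.

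The conclusion assumes ANC is per microlitre in the aplastic anaemia table. The example patients are illustrative. The factor of 1,000 rests on the platelet floor in Section 3.1, not on the aplastic anaemia limit of 20,000, which carries no unit. The direction of the signs and the platelet unit follow from the Protocol itself; the exact aplastic anaemia limits need confirming against the source guideline.

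Separately, both tables hold at G3 where Section 5.6.3 generally stops. That difference exists with or without the misprints and is not part of this point.

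**What to change.** Check both entries against the source guideline, then:

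- Aplastic anaemia G3-4: change to ANC < 200, platelets < 20,000, reticulocytes < 20,000 and marrow < 25%, and state the ANC unit.
- Immune thrombocytopenia: give G1 to G4 as < 100, < 75, < 50 and < 25, all x 10^9/L.

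The corrected aplastic anaemia row will still have no numeric limit separating G3 (hold) from G4 (permanent stop).

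The cost is four signs in one row and one unit in four rows, with no change to design, sample size or analysis.
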